8.3 Statistical Procedure for all Data

The investigators should submit completed case report forms to the CRA in a timely manner. The CRA should check the case report forms, verify the original records, and check for any omissions or errors. After ensuring there are no errors, the CRA should deliver the forms to the principal investigator. If there are any questions about the case report forms, the CRA should ask the investigators, who should respond promptly and make any necessary data modifications and confirmations.

Do not fill in missing data.

8.4 Procedure for Handling Deviation of Report from the Original Statistical Plan

Any changes to the original statistical plan should be explained and justified in the protocol and/or in the final report.

9 . Risk-Benefit Analysis

9.1 Benefits of the Study

During the trial period, the collected information can help doctors better assess patients' constipation conditions and treatments, so the patients can know their health status. Important information obtained from this study may provide information for future patients and medical staff who use such device, helping to increase their own or other patients' treatment options.

9.2 Risks of the Study

The risk of using the Vibrabot capsule during treatment is relatively low, with capsule retention being the most concerning adverse event. The current systematic review reported in international authoritative journals mentions that the retention rate of capsule devices is about 0.73% (95% confidence interval: 0.59-0.89%). There has not been a single case of capsule-related death since the use of capsule devices. Even if capsule retention occurs clinically, it can indirectly prompt patients to receive early diagnosis and treatment, and the benefits to patients are greater than the risks. If the capsule is not expelled after 14 days, an abdominal upright X-ray is required to confirm whether the capsule is retained and its approximate location. Retention is not a complication caused by the capsule but is due to the patient's hidden condition, not the quality of the capsule itself. The current methods for removing retained capsules include spontaneous expulsion, drug treatment, surgery, or endoscopic removal. Drug treatment can alleviate intestinal mucosal edema and inflammatory response, which

may cause the inflammatory stricture to recede and the retained capsule to pass spontaneously.

During the capsule vibration process, you may experience symptoms such as bloating, abdominal pain, and diarrhea. If serious adverse events occur, you can contact the investigator immediately for appropriate treatment.

10. Feasibility Analysis of the Trial

- 1) The Vibrabot capsule has been approved by the National Medical Products Administration (NMPA), and its safety and efficacy have been verified by registered clinical trials.
- 2) The common risk of capsule devices is capsule retention. In this study, the study physician has excluded subjects with contraindications to the Vibrabot capsule according to the exclusion criteria to avoid capsule retention, and the dosage of similar products approved by the FDA is five capsules/week, it is safe for the subjects in this trial to take five capsules per week.
- 3) Shanghai Changhai Hospital is a tertiary hospital with medical device clinical trial qualification and sufficient patient sources. The co-investigators have rich clinical experience and received GCP and related training. The investigators will be trained on the protocol and product details prior to the study implementation to ensure that they can strictly follow the protocol for examination and treatment, and the subjects will be required to strictly follow the physician's advice.

11. Quality Control of the Clinical Trial

Investigator's Qualification: Investigators participating in this clinical trial are qualified and have the professional background and ability to conduct this trial.

Investigator training: Prior to the start of the clinical trial, all investigators will be trained to have a full understanding of the clinical trial protocol and the specifics of each indicator.

Informed consent will be carefully executed by the investigators so that the subjects fully understand the requirements of the trial.

Clinical trial monitoring: The sponsor will appoint a CRA to pay regular monitoring visits on the implementation of the clinical trial. The CRA will check the completeness of medical records and the correctness of case report forms and verify the trial data.

Data Management: During the entire test, the main tool used is the "Vibrabot Health" electronic questionnaire to collect patients' treatment information. Patients are required to record their test data completely, truthfully, clearly, and objectively. The electronic questionnaire can directly store test data, avoiding errors from secondary transcription.

12. Ethical Issues and Informed Consent

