|-------------------------|--|
| | 
week during the follow-up phase compared to the baseline period;
 
6) Proportion of patients with an average of ≥ 3 SBMs per week during the follow-up phase;
 
7) Proportion of patients with a reduction of ≥ 1 point in total PAC-QOL and PAC-SYM scores after treatment compared to the baseline period;
 
8) Proportion of patients with a reduction of ≥ 1 point in total PAC-QOL and PAC-SYM scores after follow-up compared to the baseline period;
 
9) Time of first use of laxative or enema after a course of vibrating capsule treatment (6 weeks);
 
10) Proportion of constipated patients (including different constipation types, occupations, age groups, BMI, gender, and baseline treatment status) responding to vibrating capsule treatment and at the end of follow-up.
 |
| Safety Endpoints | 
 1. The incidence (%) and the number of device-related adverse events (AEs) and serious adverse events (SAEs); 2. The incidence (%) and the number of device defects. |

1. About the Sponsor

| | |
|--------------|---|
| Name: | ANKON Medical Technologies (Shanghai) Co., Ltd. |
| Address: | [name] |
| Contact No.: | [name] |

2. List of All Clinical Trial Sites and Investigators in the Multi-Center Clinical Trial

| Site No. | Clinical Trial Site Name | Principal Investigator | Professional Title |
|----------|---|------------------------|----------------------------|
| 01 | The First Affiliated Hospital of Navy Medical University (Shanghai Changhai Hospital) | [name] | Chief Physician, Professor |

| | | | |
|----|---|----------------|----------------------------|
| 02 | Ruijin Hospital, Shanghai Jiao Tong University School of Medicine | [name] | Chief Physician, Professor |
| 03 | Shanghai Tongji Hospital | [name] | Chief Physician |
| 04 | Shanghai Tenth People's Hospital | [name] | Chief Physician, Professor |
| 05 | Shanghai First People's Hospital | [name] | Chief Physician |
| 06 | Shanghai Sixth People's Hospital | [name] | Chief Physician, Professor |
| 07 | Shanghai Ninth People's Hospital | [name] | Chief Physician |
| 08 | Shanghai Yangpu District Central Hospital | [name] | Chief Physician |
| 09 | Shanghai Pudong New Area Gongli Hospital | [name] | Chief Physician |

3. Purpose and Content of the Clinical Trial

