7.3 Safety Evaluation Method

The safety is evaluated by the occurrence of device-related adverse events (AEs) and device-related serious adverse events (SAEs) throughout the study period.

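### Capsule retention, the risk that section 9.2 ranks first, can drop out of the safety endpoint through attribution alone

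*Combined protocol and SAP*

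**What the plan says.** Section 9.2 rates the risk of the capsule as fairly low, with "capsule retention being the most concerning adverse event". It cites a retention rate for capsule devices of about 0.73% (95% CI 0.59-0.89%). It then says "Retention is not a complication caused by the capsule", puts it down to a hidden condition in the patient, and adds that the cause is "not the quality of the capsule itself". The same section sets a clinical rule: "If the capsule is not expelled after 14 days, an abdominal upright X-ray is required". Section 10 calls retention the common risk of this type of device and, on dose, concludes that "it is safe for the subjects in this trial to take five capsules per week".

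The Protocol Summary lists two safety endpoints. The first is "The incidence (%) and the number of device-related adverse events (AEs) and serious adverse events (SAEs"; the second is "The incidence (%) and the number of device defects". Section 7.3 is more explicit on the first: "The safety is evaluated by the occurrence of device-related adverse events (AEs", and it puts the same device-related limit on serious adverse events.

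Section 13.1.2 defines five relatedness categories, from definitely related to unrelated. Section 13.1.3 requires every adverse event to be recorded on the form. Sections 13.3 and 13.4.1 define serious adverse events and their reporting route, with no relatedness condition. Retention is not named in either safety endpoint.

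**The concern.** An endpoint limited to device-related events depends on a causality judgement made case by case. For this one type of event, the protocol gives a general answer before any case has occurred, and the answer points away from the device. Section 2 lists nine sites, and they have no rule for classifying a retention. Two sites could rate the same event differently, and the endpoint table could show fewer retentions than the adverse event forms hold.

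The study is post-marketing and is meant to support consensus or guidelines on the use of the capsule (section 3.1). Readers of its safety result will look first for the rate of the risk that the protocol itself ranks highest. If that rate depends on how one or two events were attributed, the table cannot be interpreted without going back to the individual forms.

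**Working it through.** **Step 1. Can a retention leave the endpoint under the text as written?**

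- *Scope.* The Protocol Summary could be read as covering all serious adverse events. Section 7.3 removes that ambiguity by limiting both kinds of event to device-related ones.
- *For relatedness.* In 13.1.2, *Possibly related* covers a close temporal link, support in the literature, and an underlying disease that cannot be ruled out. A retention with a suspected lesion fits this well. *Unlikely related* and *Unrelated* fit poorly: a retention cannot occur unless a capsule was swallowed, and section 10 treats it as a known risk of such devices.
- *Against relatedness.* *Unrelated* also includes a clause on events explained by the patient's clinical state. Section 9.2 gives that explanation for retentions in general.
- *Cut-off.* No text says where on the five-level scale device-related begins, so even a rating of *Possibly related* does not guarantee that the event is counted.

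The scale leans one way and 9.2 the other, and nothing settles it.

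**Step 2. How many events are at stake?**

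The plan gives no expected number of retentions, so there is no figure of its own to reproduce. The efficacy sample size plays no part here.

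Inputs: N = 300 capsule patients (section 8.1); p = 0.73%, range 0.59-0.89% (section 9.2). Assumptions: p is per patient, and it applies to this screened population.

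Expected number = N × p; chance of at least one = 1 − (1 − p)^N.

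| p | Expected in 300 | Chance of at least one |
|---|---|---|
| 0.59% | 300 × 0.0059 = 1.77 | 0.831 |
| 0.73% | 300 × 0.0073 = 2.19 | 0.889 |
| 0.89% | 300 × 0.0089 = 2.67 | 0.932 |

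If screening halves the rate, the expected number is 300 × 0.00365 = 1.1.

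The documents do not say whether the rate is per patient or per capsule. At five capsules a week for 6 weeks there would be 300 × 5 × 6 = 9,000 capsules, and a per-capsule rate would give 9,000 × 0.0073 = 65.7 events (53.1 to 80.1). This is not a forecast; it shows how much the count depends on the unstated denominator.

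**Step 3. What does attribution do to the reported figure?**

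Suppose two retentions occur. The exact (Clopper-Pearson) 95% interval for x events has as its lower limit the 0.025 quantile of Beta(x, 300 − x + 1) and as its upper limit the 0.975 quantile of Beta(x + 1, 300 − x). For x = 0 the lower limit is 0 and the upper limit is 1 − 0.025^(1/300).

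| Rated device-related | Endpoint shows | Exact 95% CI |
|---|---|---|
| both | 2/300 = 0.67% | 0.08% to 2.39% |
| one | 1/300 = 0.33% | 0.01% to 1.84% |
| neither | 0/300 = 0% | 0 to 1.22% |

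The intervals overlap, and the last one still contains 0.73%. What changes is whether the named risk appears in the result at all.

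**The case against.** The strongest reply is that 13.1.2 governs attribution, while the sentence in 9.2 is risk-benefit narrative that sets no classification rule. Applied properly, the scale leads to *Possibly related*. What is left is a missing definition of device-related, which touches every adverse event and not retention alone. In addition, 13.1.3 puts all adverse events on the form, and 13.3 and 13.4 send a retention that needs hospital admission, or surgery to avoid permanent impairment, to the sponsor and the ethics committee whatever its attribution.

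Much of this stands, and it limits the point. A reader might infer that retentions would go unrecorded or be hidden; the recording and reporting rules say otherwise. A reader might also infer that the protocol formally classifies retention as unrelated; it does not. Its absence from the device-defect endpoint is not a second gap, because 13.2 gives labeling errors, quality problems and malfunctions as examples, and a working capsule that is retained is not naturally one of these. Nor can it be said that the trial has no check on expulsion. The visible schedule in 7.1 names none, but the questionnaire items are not shown and may include one.

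The reply does not close the gap between the forms and the endpoint. Expedited reporting does not put an event into the endpoint table, and under 7.3 even a serious retention leaves that table if it is rated unrelated. The exclusion criteria do not remove the issue either: criterion 2 in 6.2 covers known or suspected obstruction or stenosis, while 9.2 attributes retention to conditions that are hidden.

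**Conclusion.** The point holds as a gap in the endpoint definition. Retention will be recorded, but whether it is counted in the safety endpoint rests on a judgement that 9.2 tilts in advance and that no rule settles. On the assumption that 0.73% is per patient and applies to this population, about 2 cases are expected in 300 patients (1.8 to 2.7), with an 83% to 93% chance of at least one. Two cases could then be reported as anything from 0% to 0.67%.

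The documents do not support a stronger conclusion, such as that safety is unmonitored or that the safety result must be wrong. The efficacy analysis is untouched. This is a cheap improvement that is worth making.

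**What to change.** 1. Report X-ray-confirmed capsule retentions as a named safety result: number and proportion with an exact 95% CI, regardless of attributed relatedness.
2. Use as denominator all patients who took at least one capsule. The safety set in 8.1 is defined by randomization, which does not fit a cohort in which patients and doctors choose the treatment.
3. State in 7.3 or 13.1.2 that *Possibly related* and above count as device-related.

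Leave the 14-day X-ray rule as it stands. In particular, do not tie it to the last capsule taken. That would narrow a rule that now has no such limit and could miss an earlier capsule that stays behind while the last one passes. It would also fall outside the study for longer courses: Visit 5 is at Week 10, so a 14-day check on a last capsule taken after about Week 8 (10 − 2) comes too late, and section 3.2 allows treatment beyond 6 weeks.

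The cost is one definition sentence and one extra table. The downside for the sponsor is a safety figure that may look less favourable.

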12.1 Ethical Considerations

12.1.1 Ethics and Regulations

This trial complies with the requirements of the Declaration of Helsinki, the *Good Clinical Practice for Medical Devices*, and other applicable national laws and regulations.

12.1.2 Medical Ethics Committee

Prior to the clinical trial, the investigator submits the trial protocol, ICF, and other relevant documents to the EC of the clinical trial site and obtains EC's approval before the trial can be conducted. Any modification of the trial protocol must be approved by the EC before implementation. SAEs during the trial shall be submitted to the EC in writing in a timely manner.

12.2 Informed Consent Process

Before enrollment, the investigator must explain to the subject or his/her guardian the details of the clinical trial, including the nature, purpose, content, expected efficacy, possible AEs and countermeasures of the trial, and answer questions from the subject. Subjects are enrolled after they fully understand the trial and sign the ICF. The ICF shall be signed by the investigator and the subject or his/her guardian in duplicate, and each party keeps one copy.

13. Provisions for Reporting Adverse Events and Device Defects

13.1 Definition of Adverse Events and Reporting Requirements

Definition: An AE is any untoward medical occurrence in a clinical trial, whether or not considered device-related.

13.1.1 Severity of Adverse Events

Mild AE: Event results in perceptible signs or symptoms, not requiring discontinuation of the device and treatment;

Moderate AE: Event results in tolerable signs and symptoms, requiring treatment; does not interfere with daily activities;

Severe AE: Event results in intolerable symptoms and signs, requiring discontinuation of the device and treatment; interferes with daily activities.

Note: AE severity is used to describe the intensity of an event. An event is not necessarily an adverse event.

13.1.2 Event Relationship to the Investigational Device

Definitely related: the use of the device and the reaction occurrence follow a reasonable temporal sequence; the reaction stops, rapidly relieves, or reduces after

stopping using the device; the reaction recurs or significantly gets worse after using the device again; supported by literature; and the influence of other factors, such as underlying diseases, have been excluded.

Probably related: no repeated device use and other criteria are the same as "definitely related"; or although other devices or drugs have been used in combination, the possibility of the reaction resulting from using concomitant devices or drugs can be excluded.

Possibly related: the time of the occurrence of the reaction is closely related to the use of the device; supported by the literature; however, more than one device or drug, in this case, result in the adverse reaction, or other factors, such as underlying diseases, cannot be excluded.

Unlikely related: the time of the occurrence of the reaction is not closely related to the use of the device; the reaction does not belong to the known adverse reactions to the device, and the development of the underlying disease may have similar clinical reactions.

Unrelated: the use of the device and the reaction occurrence do not follow a reasonable temporal sequence; the reaction is not the type of adverse reaction to the device; the reaction can be explained by the patient's clinical status or other reasons; the reaction relieves or disappears after excluding the clinical symptoms or other reasons.

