diabetics, those taking opiates, antipsychotic drugs, or bedridden patients. Occupation, lifestyle, dietary habits, mental health, family history of constipation, and BMI are factors related to constipation.

Constipation affects patients' quality of life, and some patients abuse laxatives or repeatedly seek medical treatment, increasing medical costs. The main treatments for constipation are adjusting lifestyle, medication, psychotherapy, biofeedback, and surgery. However, these methods often have side effects, and patient satisfaction is still relatively low. A new approach needs to be explored to address this clinical problem.

The Disposable Gastrointestinal Vibrating Capsule System (Vibrabot capsule) (NMPA Device Approval No. 20223090282) is the world's first approved and marketed product for treating constipation through purely physical means. It can provide intermittent comfortable massages to the digestive tract, activate the intestinal neural network, awaken intestinal motility, and help alleviate constipation issues. Clinical study results show that the product is safe to use and can increase the frequency of bowel movements in patients with chronic functional constipation. This study focuses on post-marketing clinical study for patients with functional constipation of varying severity, further evaluating the efficacy of the product in a large sample population.

5. Product Features, Composition, Working Principle, and Action Mechanism

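### Section 13.1.2 requires literature support for every related grade open to a capsule-alone patient, so a previously undescribed reaction fits no grade and can be missed by the device-related safety endpoint

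*Combined protocol and SAP*

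**What the plan says.** Section 13.1.2 defines five causality grades.

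- *Definitely related* joins its conditions with 'and'. After reasonable timing and relief on stopping, the list continues: "the reaction recurs or significantly gets worse after using the device again; supported by literature; and the influence of other factors", which must have been excluded.
- *Probably related* has two limbs. The first is "no repeated device use and other criteria are the same as" the definite grade. The second covers the case where "although other devices or drugs have been used in combination, the possibility of the reaction resulting from using concomitant devices or drugs can be excluded".
- The third grade, *possibly related*, begins: "Possibly related: the time of the occurrence of the reaction is closely related to the use of the device; supported by the literature". It then adds that another device or drug, or another factor, cannot be excluded.
- *Unlikely related* requires that the timing is not close, and adds that "the reaction does not belong to the known adverse reactions to the device" and that the underlying disease could look similar.
- *Unrelated* starts from the absence of a reasonable time sequence, and also mentions a reaction that is not of the device's type.

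Section 7.3 says how the grades are used: "The safety is evaluated by the occurrence of device-related adverse events (AEs) and device-related serious adverse events (SAEs) throughout the study period". The Protocol Summary gives the endpoint as the incidence and number of such events. Neither place says which of the five grades count as device-related, and there is no rule for an event that meets none of them.

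**The concern.** Literature support is the criterion a new reaction is least likely to meet. Section 4 describes the capsule as "the world's first approved and marketed product for treating constipation through purely physical means", and a post-marketing study is a natural place to look for reactions not yet described. Here a rule on prior publication stands between such a reaction and a related grade, however strong the clinical evidence in the individual patient.

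The effect is also uneven. A patient taking other treatments has a route to 'probably related' without literature. A patient on the capsule alone, in whom attribution is cleanest, has none. Capsule-alone patients are the population of the primary efficacy endpoint (section 7.2.1), so they are not a marginal group. At stake is whether the device-related AE rate can register new reactions, and whether the nine sites listed in section 2 would grade them alike.

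**Working it through.** The documents give no figure to reproduce on this point, so the check is of the definitions. Each list of conditions is read as cumulative.

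**Step 1: the hardest case.** Take a capsule-alone patient with close timing, relief on stopping, recurrence on re-use, other causes excluded, and no literature on the reaction.

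| Grade | Literature needed? | Met? | Reason |
|---|---|---|---|
| Definitely | Yes | No | Four of five conditions met; literature missing |
| Probably, limb 1 | Yes, by reference | No | Literature missing |
| Probably, limb 2 | No | No | Needs other devices or drugs in use |
| Possibly | Yes | No | Literature missing |
| Unlikely | No | No | Timing is close |
| Unrelated | No | No | Time sequence is reasonable |

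**Step 2: all well-timed patterns without literature.** Three features can still vary: relief on stopping, recurrence on re-use, and exclusion of other causes. That gives 2 × 2 × 2 = 8 patterns for each type of patient.

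- Capsule alone: 8 of 8 fit no grade.
- Combination therapy: the 4 with other causes excluded reach 'probably related' through its second limb; the other 4 fit no grade.

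**Step 3: link to the endpoint.** Section 7.3 counts device-related events. An event with no grade has no stated place in that count. Section 13.1.3 still requires every AE to be recorded, and section 13.4.1 requires SAE reporting with no causality condition. The data therefore exist; what is unsettled is whether the event enters the endpoint.

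**Step 4: scale, by assumption only.** The documents give neither the rate of undescribed reactions nor the number of capsule-alone patients. Expected events = capsule-alone patients × true rate.

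- If all 300 planned capsule patients used it alone, assumed rates of 0.5%, 1% and 2% give 300 × 0.005 = 1.5, 300 × 0.01 = 3 and 300 × 0.02 = 6 events.
- If half did (also assumed), the counts are 0.75, 1.5 and 3.

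None of these events would meet a related grade as the text stands.

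**The case against.** The strongest reply is that an event fitting no grade is not thereby graded unrelated. An investigator looking for the nearest grade would see four of five conditions for 'definitely related' met and might well choose a related grade. This stands. A reader might infer that such events are certain to leave the endpoint, that the endpoint is blind to new reactions, or that downward bias is established. The documents do not support this, because they are silent on ungradable events and on which grades count.

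Second, 'literature' is undefined and need not mean literature on this device. Section 9.2 cites a systematic review of retention with capsule devices and names bloating, abdominal pain and diarrhea as possible. Section 10 mentions registration trials and similar approved products. This also stands: known reactions are less affected, and the gap concerns only reactions absent from any such source.

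Third, serious new events still reach the sponsor and ethics committee under section 13.4.1, and the Protocol Summary's endpoint wording could be read as counting all SAEs. The first part stands. The second is weak, because section 7.3 says device-related SAEs.

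Fourth, a reader might turn the illustration into a statement that a true 2% would be reported as 0%. That needs all six patients to be on the capsule alone and all six to be left out. Section 3.2 allows combination therapy, and the 2% is itself assumed.

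Finally, it is tempting to delete the unknown-reaction wording from 'unlikely' and 'unrelated'. In 'unlikely' that wording is an extra condition joined to poor timing, so deleting it would make the grade easier to assign. The same holds for 'unrelated' if its list is cumulative.

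**Conclusion.** The point holds as a gap in the grading rule. As written, a well-timed, previously undescribed reaction in a capsule-alone patient meets none of the three related grades and neither of the other two. It can therefore be left out of the device-related endpoint or graded inconsistently between sites. Any resulting error would tend to lower the device-related rate, because the literature condition can only keep events out of the related grades. The size cannot be estimated from the documents, and neither the primary endpoint nor the recording of AEs is affected.

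The conclusion assumes that the lists are cumulative. That is explicit for 'definitely related', but 'possibly' and 'unrelated' are separated only by semicolons. If both were read as alternatives, the same event could satisfy 'possibly related' on timing and 'unrelated' on reaction type, so grading would still be unsettled.

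**What to change.** In section 13.1.2:

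- Make literature support supporting evidence rather than a required condition for all three related grades. A close time relation should be enough for at least 'possibly related' when the device cannot be ruled out as a cause.
- State which grades count as device-related, and that an event fitting no grade counts as related.
- Keep the timing conditions in 'unlikely' and 'unrelated'. Rather than deleting the unknown-reaction clauses, state that being previously unknown is not by itself enough for either grade.

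In section 7.3 and the Protocol Summary, add a table of all AEs and SAEs regardless of causality beside the device-related rate.

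The cost is a wording change, which section 14 requires the ethics committee to approve, and one extra table from data already collected. The device-related AE rate may rise slightly. Treatment, visits and sample size do not change.
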